## List of abbreviations

AE	Adverse event
AMR	Antimicrobial resistant
aSCRIP	Adjusted Stability of cardio-respiratory in preterm infants
BVM	Bag-valve-mask ventilation
CLSI	Clinical and Laboratory Standards Institute
CONSORT	Consolidated Standards of Reporting Trials
CPAP	Continuous positive airway pressure
Cm	Centimetres
CSF	Cerebro-spinal fluid
DSMB	Data safety monitoring committee
eCRF	Electronic case report form
EC	Ethics committee
EFSTH	Edward Francis Small Teaching Hospital
ESBL-KP	Extended Spectrum Beta-lactamase producing Klebsiella pneumoniae
GCP	Good clinical practice
GNB	Gram-Negative Bacilli
HAI	Hospital acquired infection
HIC	High income country
HIV	Human Immunodeficiency virus
ICH	International Conference on Harmonization
ID	Identification
IV	Intravenous
KMC	Kangaroo Mother Care
LBW	Low Birth Weight
LMIC	Low-middle income country
LOS	Late onset sepsis
LSHTM	London School of Hygiene and Tropical Medicine
MDR	Multi-Drug Resistant
MRC	Medical Research Council
MRCG	MRC Unit The Gambia
NMR	Neonatal mortality rate
OFC	Occipito-frontal circumference
PCR	Polymerase Chain Reaction
PI	Principal Investigator
RDS	Respiratory distress syndrome
RV	Recto-vaginal

Protocol #: 1

---

SAE	Serious adverse event
SCC	Scientific Coordinating Committee
SOP	Standard operating procedure
SPO 2	Peripheral capillary oxygen saturation
SDG	Sustainable development goal
SSP	Study specific protocol
TMF	Trial Master File (regulatory file)
WHO	World Health Organization

Protocol #: 1

---

**DEFINITIONS**

Adverse event:	“Any unfavourable and unintended sign, symptom, laboratory finding or disease which was absent at baseline, or if present at baseline, appears to worsen AND is temporally associated with the participants involvement in the research”
Apnoea:	No spontaneous breathing for either 20 seconds, or less than 20 seconds and associated with colour change; hypoxia (SPO 2 <88%) or bradycardia (heart rate <100 bpm)
Low birth weight:	Birth weight 1500 - 2499g
Very low birth weight	Birth weight 1000 - 1499g
Extremely low birth weight:	Birth weight less than 1000g
Neonatal period:	Period from birth to 28 days
Early neonatal period:	0 – 6 days after birth
Late neonatal period:	7 – 28 days after birth
Neonatal mortality rate:	Number of neonates dying before 28 days of age, per 1000 live births per year
Preterm birth:	Birth at <37+0 completed weeks gestation
Extreme preterm:	Birth at <28+0 weeks gestation
Very preterm:	Birth at 28+1 – 31+6 weeks gestation
Moderate-late preterm:	Birth at 32+0 – 36+6 weeks gestation
Serious Adverse event:	Any untoward medical occurrence which:  a) Results in death b) Is life threatening (Neonatal Near Death) c) Requires prolonged hospitalisation d) Results in persistent or significant disability / incapacity

**Eligibility:**

Stable clinical condition:	SPO 2 ≥88% in room air for 10 minutes AND all of: ✓ Respiratory rate 20 – 60 breaths/min ✓ No apnoeic episodes requiring bag-valve-mask ventilation ✓ No severe chest indrawing
Mild instability:	A. SPO 2 ≥88% in air for >5 minutes AND all of: ✓ Respiratory rate 60 – 100 breaths/min ✓ No apnoeic episodes requiring bag-valve-mask ventilation ✓ No severe chest indrawing OR B. SPO 2 ≥88% in oxygen for >5 minutes AND none of: ✓ Respiratory rate 60 – 100 breaths/min ✓ Severe chest in-drawing ✓ Apnoeic episodes requiring bag-valve-mask ventilation
Moderate instability:	A. SPO 2 ≥88% in oxygen for >5 minutes AND ≥1 of: Respiratory rate >60 breaths/min ✓ Respiratory rate <20 b/min ✓ Severe chest in-drawing

Protocol #: 1

- ✓ Apnoea requiring bag-valve-mask ventilation
- ✓ HR <100 or >200 beats/min

B.  $\text{SPO}_2 < 88\%$  in oxygen for >5 minutes AND none of:

- ✓ Respiratory rate <20 or >100 breaths/min
- ✓ Severe chest in-drawing
- ✓ Apnoea requiring bag-valve-mask ventilation
- ✓ Heart rate <100 or >200 beats/min
- ✓ CPAP

Severe instability:

Either:

A.  $\text{SPO}_2 < 88\%$  in oxygen for >5 minutes

AND ≥1 of the following:

- ✓ Respiratory rate <20 or > 100 breaths/min
- ✓ Severe chest in-drawing
- ✓ Apnoea needing bag-valve-mask ventilation
- ✓ HR <100 or >200 beats/min

OR

B. *CPAP is required on clinical grounds as per Standardised Preterm Management Protocol*

Summary of stability definitions:

	Stable	Mild		Moderate			Severe	
In oxygen	No	No	Yes	Yes			Yes	CPAP**
$\text{SPO}_2^*$	$\geq 88\%$	$\geq 88\%$	$\geq 88\%$	$\geq 88\%$	$\geq 88\%$	<88%	<88%	
	AND all of:	AND all of:	And none of:	AND ≥ 1 of:	AND ≥ 1 of:	AND none of:	AND ≥ 1 of:	
Respiratory rate*	20 - 60	60 - 100		>100 or <20				
Severe chest in-drawing	No	No		Yes				
Apnoea needing BVM ventilation	No	No		Yes				
Heart rate*				<100 or >200				

\*Oxygen saturation, heart rate and respiratory rate classified according to those present for ≥5 out of 10 minutes observation. If the values are present for 5/10 minutes classify the baby in the less severe category. E.g. If oxygen saturation is in range  $\geq 88\%$  for 5 minutes and <88% for 5 minutes the baby is classed as having oxygen saturation of  $\geq 88\%$

\*\*If CPAP is required baby is classed as severely unstable, regardless of oxygen saturation. The decision to start CPAP is made according to the Standardised Preterm Management Protocol.

Major congenital malformation: A malformation which is present at birth and which is incompatible with life or requires immediate surgical management

Severe jaundice: Jaundice occurring within the first 24h after delivery and/or visible in sclera, palms or soles

Protocol #: 1

---

**Interventions:**

Kangaroo mother care:	Package of care consisting of prolonged skin to skin contact between baby and caregiver (usually mother); promotion of exclusive breast milk feeding and early hospital discharge with close follow up
Continuous KMC:	Skin-to-skin contact between baby and caregiver for at least 18h/day
Intermittent KMC:	Skin-to-skin contact between baby and caregiver for periodic times of at least 1h duration per session
Early continuous skin-to-skin contact	Skin-to-skin contact between baby and mother/caregiver for at least 18h/day and starting within 24h of birth

**Outcomes**

All-cause mortality: Death of a neonate due to any reason within a defined time period

Suspected late onset infection: New onset of any 1 of the following at > 72h of age:  
Pallor; Lethargy; Jaundice; Apnoea; Hepatomegaly

Confirmed late onset infection: New onset of any 1 of the following at > 72h of age:  
Pallor; Lethargy; Jaundice; Apnoea; Hepatomegaly  
AND blood or CSF culture positive for known neonatal pathogen

Hypoglycaemia: Blood sugar level < 2.6 mmol/l, as measured by bedside testing

Hypothermia: Auxillary temperature less than the normal range (36.5°C – 37.5 °C)

Mild hypothermia: 36.0 °C – 36.4 °C

Moderate hypothermia: 32.0 °C – 35.9 °C

Severe hypothermia: <32.0 °C

Hypothermia density: Proportion of time temperature <36.5 °C during a defined time period

Duration of admission: Time from hospital admission to discharge

Protocol #: 1

---

## Protocol summary

Title:	A randomised controlled trial of early continuous skin-to-skin contact versus standard care on survival of hospitalised unstable neonates <2000g in The Gambia
Alias :	eKMC
Population:	392 hospitalised mild-moderately unstable neonates weighing <2000g and aged 1 – 24h
Number of participants:	392 newborns (ratio 1:1)
Number of Sites:	1 recruitment site
Location of Sites (including satellite sites):	Neonatal unit at Edward Francis Small Teaching Hospital, Banjul, The Gambia
Trial Duration:	Recruitment over period of 24 months
- Clinical Phase:	Whole trial: 25 months
Duration for Participants:	Neonates will be followed up from enrolment within 24h after birth to 28 days Mothers/caregivers will be consented for paired biological swab samples at/shortly after admission
Description of intervention:	Kangaroo mother care is a package of care for preterm/low birth weight (LBW) neonates consisting of: prolonged skin to skin contact; promotion of early & exclusive breast milk feeding; early hospital discharge with close follow up. Intervention arm: Subjects will receive the continuous skin-to-skin contact aspect of KMC as soon as possible within 24h after admission Control arm: Subjects will be managed in incubators or radiant heaters, as per standard care, with skin-to-skin contact (KMC) started when clinically stable at >24h of admission
Objectives:	Objective 1. To assess the effect of early continuous skin-to-skin contact on survival of hospitalised, mild-moderately unstable neonates weighing <2000g  Objective 2. To assess the effect of early continuous skin-to-skin contact on other important clinical outcomes for hospitalised, mild-moderately unstable neonates weighing <2000g  Objective 3. To assess the safety of early continuous skin-to-skin contact in the hospital management of mild-moderately unstable neonates <2000g

Protocol #: 1

---

Objective 4. To explore early (thermal control, cardio-respiratory stability) and late (infection prevention control, gastro-intestinal stability) mechanistic pathways for the beneficial effects of early continuous skin-to-skin contact compared to standard care in hospitalised, mild-moderately unstable neonates weighing <2000g.

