# 2 STUDY OBJECTIVES & OUTCOMES

## 2.1 Objectives

**Objective 1. To assess the effect of early continuous skin-to-skin contact on survival of hospitalised, mild-moderately unstable neonates weighing <2000g**

This will be achieved by measurement of the primary outcome of mortality at 28d and secondary outcomes of time to death..

**Objective 2. To assess the effect of early continuous skin-to-skin contact on other important clinical outcomes for hospitalised, mild-moderately unstable neonates weighing <2000g**

This will be achieved by measurement of the following secondary outcomes:

- Growth (weight)
- Duration of hospital admission

Protocol #: 1

---

- Suspected late onset infection

**Objective 3. To assess the safety of early continuous skin-to-skin contact in the hospital management of mild-moderately unstable neonates <2000g**

This will be achieved by measurement of the following secondary outcomes:

- Cardio-respiratory stability at 24h

**Objective 4. To explore causal pathways for the beneficial clinical effects of early continuous skin-to-skin contact compared to standard care in hospitalised, mild-moderately unstable neonates weighing <2000g**

This will be achieved by measurement of the following secondary process outcomes:

- Time to mortality
- Cardio-respiratory stability at 24h (early pathway)
- Hypothermia (early or late pathway)
- Exclusive breastmilk feeding at discharge (late pathway)
- Prevalence of intestinal ESBL-Klebsiella pneumoniae carriage (samples to be taken and stored, pending future funding)
- In addition and also as part of objective 4, carriage swab samples, environmental samples and blood/CSF culture isolates will be stored with the intention of undertaking the following work at a future stage, once additional funding is secured:
  1. Explore the effect of early skin-to-skin contact on neonatal intestinal/rectal microbiome, with comparison to maternal/caregiver microbiomes (16SrRNA)
  2. Describe the molecular epidemiology of ESBL-KP isolates, including clonal diversity and antibiotic resistance profile (whole genome sequencing)
  3. Compare neonatal carriage and invasive isolates with environmental isolates and maternal/caregiver carriage isolates to explore transmission of neonatal pathogens (whole genome sequencing)

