### **3. Study design**

#### **3.1 Type of study and design**

This individually randomised, controlled, superiority trial will compare 2 parallel groups of hospitalised preterm/LBW newborns receiving either early continuous skin-to-skin contact (started at 1 - 24h after birth)(intervention group) or standard care and late KMC (started at >24h) once clinically stable (control group) (ratio 1:1). The intervention will be un-blinded to participants and researchers with blinding to outcomes, where possible. Interventions will be maintained until hospital discharge and encouraged post-discharge with daily in-patient review and follow up at 28 days. If participants meet criteria of being severely unstable (definitions, page 10) whilst receiving the intervention they will revert to standard care and re-commence KMC when stability criteria are met, in accordance with current standard care (section 7). Primary analysis of primary and secondary outcomes will be on an intention to treat basis. A pragmatic study design will be used with a standardised preterm/LBW clinical management protocol based on current standard care and provided by study site staff. In-order to explore the infection prevention control mechanisms underpinning this intervention, paired maternal /caregiver swab samples will be taken at time of admission in addition to environmental swab samples.

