**5.5.3 Microbiological data**

The baseline neonatal rectal and skin swabs will be taken as soon as possible after enrolment, before starting the intervention or control procedures and prior to administration of antibiotics, unless the clinical situation warrants immediate antibiotic therapy.

Paired maternal/caregiver skin and recto-vaginal (RV)(mothers only) swabs will be taken as soon as possible after admission and prior to the neonate commencing the intervention or control procedures. If the mother is not immediately available maternal swabs will be taken before the mother starts any skin-to-skin intervention.

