### **5.7.3 Control arm**

Babies allocated to the control arm will be placed in an incubator or under a radiant heater, as per standard management at the study site. They will wear a hat and be wrapped as per standard care. Oxygen will be provided from an oxygen concentrator and IV fluids securely attached to the IV cannula and drip rate calculated, as in the intervention arm. The pulse oximeter will be placed inside the incubator or next to the radiant heater. The parent/caregiver will be able to touch the baby, if requested, but will not provide any skin-to-skin contact until he/she meets stability criteria (definitions, page 10) and is >24h since hospital admission, in keeping with current standard care practices at the study site. The baby will initially receive intermittent KMC (60 minutes after feeds) with the parent/caregiver in a chair next to the incubator or radiant heater in the study area. Once fully stable (definitions, page 10) and not requiring oxygen or IV fluids, the baby will be transferred to the KMC Unit to start continuous KMC.

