**14.5.3 Informed consent for maternal swabs/caregiver swabs**

Written informed consent for obtaining maternal/caregiver swabs will be taken after consent for the neonates participation but prior to any maternal/caregiver samples being obtained. All participants will have the option of declining to have a particular swab taken (E.g. recto-vaginal) if they are not comfortable with the procedure.

Within the intervention arm, consent will be taken from the person providing initial KMC, which is expected to be the mother in most cases but may be another female family member or the father. If the mother later becomes available to provide KMC, she will be asked to provide informed consent for repeat swab samples at time of commencing skin-to-skin contact.

Figure 3. Flow chart for obtaining informed consent for neonatal participation in eKMC study

Protocol #: 1

---

Obtaining the maternal/caregiver samples will not delay starting the intervention. For subjects allocated to the control group, informed consent for swab samples will be taken from the mother or caregiver prior to the subject receiving any skin-to-skin contact (table 3).

Table 3. Outline of consent process for mothers/caregivers providing biological samples

Study arm	Scenario	Consent taken from	Purpose of consent	Timing
Intervention	Mother present at time of recruitment	Mother	Recto-vaginal swabs Skin swabs	Before commencing intervention
	Another caregiver present at time of recruitment (E.g. Father/aunty/grandmother)	Caregiver who is present & providing skin-to-skin contact	Skin swabs	
		Mother once available	Recto-vaginal swabs Skin swabs	prior to starting skin-to-skin contact
Control	Mother present at time of recruitment	Mother	Recto-vaginal swabs Skin swabs	Before commencing any skin-to-skin contact
	Another caregiver present at time of recruitment (E.g. Father/aunty/grandmother)	No consent for biological samples taken. Wait for mother to be present or baby ready to start skin-to-skin contact with person other than mother	Skin swab	Before commencing any skin-to-skin contact
		Mother once available	Recto-vaginal swab Skin swab	As soon as possible after mother available and prior to starting any skin-to-skin contact

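### Section 14.5.3 ties control-arm paired caregiver swabs to first skin-to-skin contact, while sections 3.1 and 5.5.3 and Appendix I place them near admission in both arms; the firm clash is the non-mother caregiver present at recruitment.

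*Protocol*

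**What the plan says.** Several places give one time, near admission, without regard to arm.

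- The Protocol summary, on consent: "Mothers/caregivers will be consented for paired biological swab samples at/shortly after admission".
- Section 3.1, on sampling: "paired maternal /caregiver swab samples will be taken at time of admission".
- Section 5.5.3 says paired maternal/caregiver swabs "will be taken as soon as possible after admission and prior to the neonate commencing the intervention or control procedures". Its one exception is for a mother who is not immediately available: her swabs may wait until just before her own skin-to-skin contact. The exception is not limited to one arm.
- Appendix I lists the paired swabs among baseline data, within 24h.

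Section 14.5.3 uses a different clock. In its Table 3, intervention dyads are sampled before the intervention starts. For controls the text says "informed consent for swab samples will be taken from the mother or caregiver prior to the subject receiving any skin-to-skin contact". Where a control baby has a caregiver other than the mother at recruitment, Table 3 says "No consent for biological samples taken. Wait for mother to be present or baby ready to start skin-to-skin contact with person other than mother". Table 1 in section 6.2 also times maternal and caregiver swabs by the start of KMC.

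The start of skin-to-skin contact differs by design. Under section 5.7.3 the control-arm parent or caregiver "will not provide any skin-to-skin contact until he/she meets stability criteria (definitions, page 10) and is >24h since hospital admission".

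The samples serve Objective 4. Section 2.1 lists, for a future stage once additional funding is secured: "Explore the effect of early skin-to-skin contact on neonatal intestinal/rectal microbiome, with comparison to maternal/caregiver microbiomes (16SrRNA". It also lists tracing transmission between baby, caregiver and environment.

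**The concern.** A paired swab is useful in a by-arm comparison only if it is taken at a comparable time in both arms and is missing for comparable reasons. Under section 14.5.3, an intervention caregiver is sampled at the start. A control caregiver may be sampled days later, after more exposure to the hospital, or never if the baby dies or does not stabilise.

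A difference between arms in how closely baby and caregiver organisms match could then reflect later sampling and selection of surviving controls, not skin-to-skin contact. An admission sample that was not taken cannot be recovered.

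**Working it through.** **The passages side by side**

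| Situation at recruitment | Section 5.5.3 and Appendix I, both arms | Table 3, intervention | Table 3, control | Can both be followed? |
|---|---|---|---|---|
| Mother present | Soon after admission, before either arm's procedures, within 24h | Before the intervention | Any time before first skin-to-skin contact | Yes, if swabbed early; Table 3 allows delay but does not require it |
| Mother absent, other caregiver present: caregiver's skin swab | As above | Taken before the intervention | Not taken; wait | No |
| Mother absent: her own swabs | Before her own skin-to-skin contact | Once available, before her skin-to-skin contact | As soon as possible once available, before skin-to-skin contact | Yes |

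The second row is the firm clash. In the first row, if the 24h in Appendix I is read as time from admission, the Table 3 control deadline always falls later, because section 5.7.3 bars contact until after 24h.

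**Scale**

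The documents give no figure for the completeness or timing of paired swabs, so there is none to reproduce. Inputs for a rough range:

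- Control arm: 392 / 2 = 196 (Protocol 10.1, 1:1).
- Control mortality at 28 days: 48% (Protocol 10.1).
- No parent within 24h of admission: 21% (Protocol 5.4.2), used here as the share with only another caregiver at recruitment.
- Share of control deaths before first skin-to-skin contact: not given. Assumed range 10% to 71%. The upper value is the feasibility study's share of deaths in the first week, 10/14 (Protocol 1.1).

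Control babies with no parent present: 0.21 × 196 = 41.2.

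Deaths among them, at the same mortality: 0.48 × 41.2 = 19.8.

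Deaths before first contact:

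- low: 0.10 × 19.8 = 2.0
- high: (10/14) × 19.8 = 14.1

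That is about 2 to 14 control pairs, or 1% to 7% of the arm (2.0/196 and 14.1/196), with no paired sample. It assumes that no mother arrives and is swabbed before the death.

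If staff also deferred swabs of control mothers who are present, the base would be all control deaths: 0.48 × 196 = 94.1. The range would be 0.10 × 94.1 = 9.4 to (10/14) × 94.1 = 67.2, or 5% to 34% of the arm. Table 3 permits this but does not call for it.

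**The case against.** The strongest reply is that Table 3 outlines consent and gives a latest point, while section 5.5.3 is the sampling instruction. A team that follows 5.5.3 breaches nothing in Table 3 when the mother is present. This stands.

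Second, 5.5.3 defers an absent mother's swabs in both arms, and only mothers give recto-vaginal swabs, so an intervention baby who dies before the mother arrives lacks that sample too. This also stands.

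Third, the control rule has a rationale: Table 1 samples the person about to give contact, and a relative present at recruitment may never do so. That explains the rule but does not remove the conflict with 5.5.3, which covers caregiver swabs before control procedures as well.

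Fourth, nothing planned depends on these samples. They are stored for future funded work, and the SAP has no maternal or caregiver swab analysis. This stands and limits the weight of the point.

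A reader might infer that 67 to 94 control dyads (first-week deaths to all control deaths) would lose their samples. The documents do not support that. It treats every control mother as absent or deferred, and the share of deaths that precede first contact is not stated.

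A reader might also infer that caregiver swabs must precede randomisation. The opening of section 5.5 says so for baseline data in general, but 5.5.3 and Appendix I do not say it of these swabs. Section 14.5.3 adds that obtaining them will not delay the intervention.

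**Conclusion.** The protocol contains two sampling clocks for the paired maternal/caregiver swabs, and the one in section 14.5.3 depends on the allocated arm. They conflict outright for the non-mother caregiver present at recruitment. For a control mother who is present, the later time is permitted only; for an absent mother, deferral is planned in both arms.

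On the stated assumptions, about 2 to 14 control pairs would have no paired sample, and more only if swabs of present mothers are also put off. The 21% is itself approximate: section 1.1 applies the same figure to absent caregivers, and a baby with no caregiver could not be enrolled.

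The consequence is confined to the exploratory Objective 4 dyad comparison. Neonatal swabs are due on days 0, 7 and 28 in both arms, so 28-day carriage is not touched by this conflict, and neither are mortality or any SAP analysis.

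**What to change.** Amend section 14.5.3, its Table 3 and Table 1 to the clock in section 5.5.3 and Appendix I, in both arms:

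- swab the mother, or the caregiver present if she is absent, as soon as possible after admission and within 24h, without delaying the intervention;
- swab a mother who arrives later at first availability, in either arm.

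Record the time of each swab. Report sampling time and missing pairs by arm. Restrict any by-arm dyad comparison to samples taken in the common window.

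The cost is protocol wording and a few extra caregiver skin swabs in controls, some from people who may never give skin-to-skin contact. The SAP describes the trial as conducted from May 2018 to April 2020, so for samples already stored only the reporting and the common-window restriction can still be applied.
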